3.7.5. Exploratory Endpoints

Exploratory endpoints during the double-blind treatment period are:

- Change from baseline in cigarette use questionnaire during the double-blind treatment period
- Change from baseline in Personal and Social Performance (PSP) score during the double-blind treatment period
- Time from randomization to the discontinuation of the study drug during the double-blind treatment period

Cigarette use questionnaire and PSP score (results and change from baseline) will be summarized using descriptive statistics at each visit in the double-blind treatment period.

Time from randomization to the discontinuation of the study drug during the double-blind treatment period will be compared between ALKS 3831 and olanzapine for the safety population, similar to [Section 3.7.2.1](#).

3.8. Safety Analysis

3.8.1. Adverse Events

Adverse events will be coded by System Organ Class and Preferred Term using the Medical Dictionary for Regulatory Activities Version 18.0 (MedDRA®). The verbatim term will be included in the AE listings.

An AE (classified by preferred term) will be considered as treatment-emergent AE (TEAE) if the event is newly occurring or worsening on or after the first dose of study drug.

A TEAE will be summarized for the open-label olanzapine population in the open-label olanzapine period, and for the ALKS 3831 populations in the ALKS 3831 period.

TEAE will be summarized by treatment group for the safety population in the double-blind period. A TEAE will be summarized in the double-blind period if it starts between the date of the

first dose of study drug (inclusive) and the date of the last dose of samidorphan or placebo in the double-blind period.

The number and percentage of subjects reporting TEAEs in each treatment group during the double-blind period will be presented by treatment group and the following categories:

- system organ class and preferred term
- preferred terms in decreasing frequency
- system organ class, preferred term, and severity
- system organ class, preferred term, and relationship
- system organ class, preferred term for drug-related TEAEs

If more than one AE is coded to the same preferred term for the same subject for the same period, the subject will be counted only once for that preferred term using the most severe and most related occurrence for the summarization by severity and by relationship to the study drug.

The incidence of most frequently reported ($\geq 5\%$ of subjects in any treatment group) TEAEs for the double-blind period will be summarized by system organ class, preferred term, and treatment group and will be sorted by decreasing frequency for ALKS 3831 group. It will also be summarized by the olanzapine dose level at randomization.

Newly-emergent AEs (NEAEs), defined as AEs that started or worsened after the date of the last dose of study drug during the treatment period will also be summarized for the follow-up safety population.

The number and percentage of subjects who have serious adverse events (SAE) will be summarized by preferred term and overall for open-label periods. It will be summarized by preferred term and treatment group for the double-blind period and will be sorted by decreasing frequency for ALKS 3831 group. A listing of subjects with SAEs for entire study will be provided by period. The number and percentage of subjects who have AEs leading to premature discontinuation from the study will be summarized in the same way as SAEs.

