countries have classified samidorphan as a controlled substance, but others have not. Sites will be given handling and storage instructions applicable to their country to ensure compliance with local regulations for controlled substances.

Reference Therapy Dosage, Duration, and Mode of Administration:

Placebo consists of tablets identical in size and appearance to the samidorphan tablets but without active samidorphan. Subjects who are randomized to olanzapine plus placebo will take these study drugs orally, once daily at the same time for 9 to 15 months.

Duration of Study:

The duration of the study period for a given subject will be approximately 12 to 18 months which includes up to 30 days for screening, a total of 6 weeks of open-label treatment, a 9 to 15 month double-blind treatment period, and 3 weeks for safety follow-up.

Primary Efficacy Measure:

The primary efficacy measure will be an event of exacerbation of disease symptoms (EEDS) based on the occurrence of pre-specified events indicative of exacerbation of disease symptoms, as confirmed by an independent adjudication committee (IAC). These events are pre-specified in the body of the protocol.

Other Efficacy Measures:

In addition to the primary efficacy measure, efficacy will be evaluated with the following measures:

- Pre-specified psychosocial events indicative of exacerbation of disease symptoms
- PANSS
- CGI-S
- CGI-Improvement (CGI-I)
- TLFB assessment of alcohol drinking
- Visual Analog Scale (VAS) for perception of desire for alcohol

Safety Assessments:

Safety will be evaluated with the following measures:

- Adverse events (AEs)
- Columbia-Suicidal Severity Rating Scale (C-SSRS) results
- Vital signs
- Clinical biochemistry, hematology, and urinalysis
- Electrocardiograms (ECGs)
- Weight
- Abnormal movement rating scales results [Abnormal Involuntary Movement Scale (AIMS), Barnes Akathisia Rating Scale (BARS), Simpson-Angus Scale (SAS)]

Statistical Methods

Efficacy:

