5.3. Dose Selection

Clinical and nonclinical safety and efficacy data support the selection of a once-daily 10 mg dose for the samidorphan component of ALKS 3831 in this study. In a prior study in alcohol-dependent subjects, samidorphan 10 mg showed the largest reduction in drinking behavior. Furthermore, clinical trial experience to date has shown samidorphan 10 mg to be well-tolerated.

This study includes a 2-week open label ALKS 3831 period. This open-label ALKS 3831 period is included because previous clinical studies have shown that the majority of AEs associated with samidorphan occur within the first 2 weeks of treatment. Starting all subjects on samidorphan not only establishes similar pharmacological states in the 2 groups prior to randomization but also mitigates the risk of functional unblinding because of subjects not tolerating study drug during samidorphan initiation. Both open-label periods (olanzapine and ALKS 3831) will allow investigators to address tolerability issues prior to randomization.

For all subjects, the once-daily olanzapine dose level throughout the study will be determined individually by the principal investigator (PI) or designee according to current clinical practice.

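### SAP 3.8.1 places a TEAE in the double-blind by-arm tables by start date alone, so an open-label event that worsens after randomization can be left out

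*SAP*

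**What the plan says.** SAP 3.8.1 contains three statements that bear on this point.

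- **TEAE definition.** An event is treatment-emergent "if the event is newly occurring or worsening on or after the first dose of study drug".
- **Double-blind rule.** The sentence opens: "A TEAE will be summarized in the double-blind period if it starts between the date of the". It then names the two ends of the window, which are the "first dose of study drug (inclusive) and the date of the last dose of samidorphan or placebo in the double-blind period". Worsening is not mentioned. The tables concerned are described as follows: "TEAE will be summarized by treatment group for the safety population in the double-blind period".
- **Post-treatment definition.** Newly emergent AEs (NEAEs), reported for the follow-up safety population, are "defined as AEs that started or worsened after the date of the last dose of study drug during the treatment period".

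The Protocol synopsis gives "a total of 6 weeks of open-label treatment" before randomization: 4 weeks of olanzapine, then 2 weeks of ALKS 3831. Protocol 5.3 explains the second part by noting that "previous clinical studies have shown that the majority of AEs associated with samidorphan occur within the first 2 weeks of treatment".

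**The concern.** The definition and the post-treatment rule both name worsening; the rule that decides what is compared between arms does not. Read literally, an event with open-label onset is counted if it worsens just after the last dose, but is not counted by arm if it worsens while the subject is taking randomized drug. No reason is given for the difference.

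The design makes this more than a drafting point. Safety and tolerability is the only secondary objective (Protocol 6.2), and the double-blind period is the only one with a randomized comparison. All randomized subjects arrive with 6 weeks of exposure, including the 2 weeks of samidorphan in which the Protocol expects most samidorphan AEs. Protocol 7.3 sets no randomization criterion that excludes an ongoing AE, so run-in events can continue into a double-blind period of 9 to 15 months. The severity table is the most exposed, because a higher grade reached after randomization is what would be missed.

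**Working it through.** The plan gives no figure to reproduce. The check applies the rules to cases and then looks for any text that closes the gap.

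**Inputs**
- SAP 3.8.1: the three statements above, and the rule that a subject counts once per preferred term within a period, at the most severe occurrence.
- SAP 3.1: baseline is defined per period, with the first double-blind dose at Visit 8. This supports reading the start of the window as the first double-blind dose, although the rule itself does not say so.
- SAP 6.1, Table 8: Visit 6 is Day 1 and Visit 8 is Day 15.
- Protocol synopsis: 4 + 2 = 6 weeks of open-label treatment.

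**Step 1: four kinds of event**
- (a) Starts in the double-blind window: a TEAE, counted by arm.
- (b) Starts in the open-label run-in and does not worsen: not counted by arm, as one would want.
- (c) Starts in the run-in and worsens on double-blind drug: a TEAE through worsening, but its start precedes the window, so it is not counted by arm.
- (d) Starts on treatment and worsens after the last dose: counted as an NEAE.

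Case (c) is the gap.

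**Step 2: an illustrative record (days invented)**
A mild event starts on Day 5 and becomes severe on Day 40, with the subject still on double-blind drug.
- TEAE test: the worsening on Day 40 is after the first dose. Met.
- Window test on one record: the start on Day 5 is 15 − 5 = 10 days before the first double-blind dose. Not met.
- Window test if the worsening is a new record: the start on Day 40 is after Day 15. Met.

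The result depends on how worsening is recorded.

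**Step 3: does any other text settle it?**
- Protocol 13.1 addresses recording of worsening only for conditions present before consent.
- Protocol 13.4 asks for an intensity assessment and for follow-up to resolution or stability. It does not require a new record or a dated change in severity.
- Protocol 14.5 asks for TEAE summaries by period and treatment group and gives no rule for assigning a worsened event to a period.
- The once-per-term rule works within a period, so it cannot recover an event assigned to an earlier one.

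None of these closes the gap.

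**Step 4: size**
The share of an arm affected is (fraction with an AE ongoing at Visit 8) × (fraction of those that worsen on double-blind drug) × (fraction of worsenings not entered as new records). The documents give none of the three, so no number follows.

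**The case against.** The strongest reply is that the loss depends on a recording convention that the documents leave open. Both the TEAE and the NEAE definitions need to know that an event worsened after a given date, so the data must date worsening somehow, perhaps by a new record. SAP 3.8.1 also expects several AEs under one preferred term in one subject. Dataset and programming specifications are separate documents (SAP 6 and 8). One could also read the start of a TEAE as the day it became treatment-emergent, which for a worsened event is the day it worsened.

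This makes the loss conditional, and that part stands. It does not remove the inconsistency. The NEAE definition lists worsening alongside starting, which counts against reading a start as including a worsening. A programmer working from the SAP alone would code the start date.

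Three stronger inferences are tempting, and the documents do not support them.

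- **That the rule flatters ALKS 3831.** Only that arm continues samidorphan, so one might expect the lost worsenings to fall there. But Protocol 5.3 says when samidorphan AEs occur, not that they persist or worsen. The same section says the run-in lets investigators address tolerability, and Protocol 8 allows subjects who do not tolerate ALKS 3831 to be discontinued before randomization. Olanzapine continues in both arms. Protocol 5.2.1 reports less weight gain with the combination in healthy adults, so a weight-related event that began in the run-in could worsen more on olanzapine plus placebo. Omitting it would favour the comparator.
- **That a count per arm can be given.** Any such count would rest on assumed fractions alone.
- **That all by-arm safety tables are affected.** SAP 3.8.1 does not expressly apply the start-date rule to serious AEs or AEs leading to discontinuation. Disposition (SAP 3.3), time to discontinuation of study drug (SAP 3.7.5), and the laboratory, weight, vital-sign, ECG, movement-scale and C-SSRS summaries do not depend on it. The events also remain in the AE listings and can appear in the open-label summaries.

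**Conclusion.** The inconsistency holds on the wording of SAP 3.8.1. An event with open-label onset that worsens on randomized drug is a TEAE by definition, yet it is left out of the double-blind by-arm TEAE incidence and severity tables.

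The conclusion rests on two conditions. First, a worsening does not open a new record with its own start date; the documents are silent. Second, the window opens at the first double-blind dose, which SAP 3.1 makes the natural reading. If the window opened at the first open-label dose instead, every open-label-onset TEAE would enter the by-arm tables. That is a different error, and the same sentence would need correcting.

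Neither the number of events affected nor the net direction of any bias can be determined from the documents. The point is confined to the double-blind TEAE tables. It is worth correcting before unblinding because it touches the only randomized comparison of TEAEs and costs very little.

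**What to change.** Replace the assignment sentence in SAP 3.8.1 with a rule to this effect: a TEAE belongs to the double-blind period when it starts, or worsens in severity, on or after the date of the first dose of double-blind study drug and no later than the date of the last samidorphan or placebo dose in that period; a worsened event is counted at its worsened severity. Add that a worsening is either dated or entered as a new AE record, so that the rule can be programmed.

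This brings the rule into line with the SAP's own TEAE definition and settles which first dose is meant. No separate criterion for an event becoming serious is needed, since that definition contains none.

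The cost is one SAP sentence, a programming rule and, if worsening is not already dated, an eCRF completion note. No new analysis is required.

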9. TREATMENT OF SUBJECTS

9.1. Study Drug Dose and Administration

Study drugs include samidorphan and matching placebo tablets, and olanzapine tablets, all for oral administration.

For all subjects, open-label samidorphan 10 mg will be taken once daily for 2 weeks prior to randomization. For subjects in the double-blind treatment period, samidorphan 10 mg (or placebo) will be taken once daily for up to 15 months.

For all subjects, the dose of olanzapine will be taken once daily (to be taken at the same time as samidorphan/placebo) at an individualized dose level. Olanzapine initiation, including transition from another antipsychotic (as applicable), is a highly individualized process. Formalizing the potential clinical scenarios may pose undue burden and/or risk to subjects. Clinical judgment is essential, and for this reason, the details of this process are left to the discretion of the treating physician, who will follow current clinical practice.

All subjects will be administered olanzapine for 11 to 17 months as part of this clinical trial.

ALKS 3831 should be taken as close to bedtime as possible. Subjects should not drive or operate heavy machinery until they know how ALKS 3831 will affect them.

After Visit 5, the dose level of olanzapine will be fixed, and an increase in dose level above the dose set at Visit 5 prior to randomization may cause the subject to be discontinued. The olanzapine dose level may be decreased at any time if the PI considers it medically beneficial to the subject, such as when a subject has stable psychiatric symptoms with side effects that may be reduced if the olanzapine dose level is decreased. If the PI decreases the dose level after randomization, only an increase above the dose level at randomization will be considered an EEDS.

At study drug dispensation visits, all subjects will receive blister cards containing samidorphan or placebo for self-administration; subjects will also receive olanzapine in separate packaging. Subjects will be instructed to take 1 tablet per day from the blister card in addition to their olanzapine tablet(s) once daily in the evening or at bedtime. The subject will take the final samidorphan/placebo dose the night before the final visit of the double-blind treatment period. Olanzapine dosing will continue uninterrupted through the end of the study. Any subject who prematurely discontinues from the study will be asked to return to the clinic for an ET visit and 2 safety follow-up visits.

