3.2.3. Safety Population

The safety population is defined as all randomized subjects who receive at least 1 dose of study drug (olanzapine, samidorphan or placebo) during the double-blind placebo-controlled treatment period.

Follow-up safety population is defined as subjects who entered into the follow-up period or have any newly emergent adverse events ([Section 3.8.1](#)).

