6.1. Analysis Visit Windows

Scheduled analysis visits are visits upon scheduled time points as specified in the protocol ([Table 1-3 Schedule of Visits and Assessments](#)).

Scheduled analysis visits during the study period will be the same as the nominal visits collected in eCRF. There will be one valid value of assessment kept for each scheduled analysis visit in summary/analysis statistics.

Unscheduled visits are visits with data not collected on the scheduled time point. Unscheduled visits will not be used for by-visit summary/analysis statistics unless specified otherwise.

All unscheduled visits will be included as collected in eCRF in listings.

The V38/ET visit can be mapped to a scheduled visit and be used for analysis and summaries only if there is no valid value already at the mapped visit.

A mapped V38/ET visit will be treated as a scheduled visit to be included in table summaries. Otherwise, it will be treated as an unscheduled visit.

Four rules will be used to map an ET visit.

- First, a 7-day (inclusive) window (\leq last dose date + 7) will be used to determine if the assessment at the ET visit is considered to be an on-treatment result. If an ET visit is within 7 days after the last dose of samidorphan/placebo, it will be considered as a valid on-treatment visit.
- Second, visit windows (inpatient stay is excluded) will be applied to determine to which visit a V38/ET valid on-treatment assessment can be mapped to. Visit windows are defined in Table 8 below.

Table 8: Visit Window Definition

Analysis Visit to be Mapped to	Target Study Day	Visit Day	Visit Window
Visit 2	Study day -28	Day -28	[-28, -25]
Visit 3	Study day -21	Day -21	[-24, -18]

Table 8: Visit Window Definition (Continued)

Analysis Visit to be Mapped to	Target Study Day	Visit Day	Visit Window
Visit 4	Study day -14	Day -14	[-17,-11]
Visit 5	Study day -7	Day -7	[-10, 0]
Visit 6	Study day 1	Day 1	1
Visit 7	Study day 8	Day 8	[2, 11]
Visit 8	Week 3	Day 15	[12, 21]
Visit 9	Week 5	Day 29	[22, 35]
Visit 10	Week 7	Day 43	[36, 57]
Visit 12	Week 11	Day 71	[58, 85]
Visit 14	Week 15	Day 99	[86, 113]
Visit 16	Week 19	Day 127	[114, 141]
Visit 18	Week 23	Day 155	[142, 169]
Visit 20	Week 27	Day 183	[170, 197]
Visit 22	Week 31	Day 211	[198, 225]
Visit 24	Week 35	Day 239	[226, 253]
Visit 26	Week 39	Day 267	[254, 281]
Visit 28	Week 43	Day 295	[282, 309]
Visit 30	Week 47	Day 323	[310, 337]
Visit 32	Week 51	Day 351	[338, 365]
Visit 34	Week 54	Day 379	[366, 393]

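### Double-blind TEAE tables stop on the date of the last bedtime samidorphan/placebo tablet, so adverse events starting the next day are moved out of them

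*SAP*

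**What the plan says.** - **TEAE window.** SAP 3.8.1 decides by onset date whether a TEAE belongs to the double-blind period, with these limits: "first dose of study drug (inclusive) and the date of the last dose of samidorphan or placebo in the double-blind period".
- **Time of dosing.** Protocol 9.1 tells subjects to take the tablets "once daily in the evening or at bedtime" and adds that "ALKS 3831 should be taken as close to bedtime as possible". For those who finish, "The subject will take the final samidorphan/placebo dose the night before the final visit of the double-blind treatment period".
- **On-treatment assessments.** SAP 6.1 accepts an early-termination (ET) visit as on-treatment if it falls "within 7 days after the last dose of samidorphan/placebo".
- **SAEs and AEs leading to discontinuation.** For SAEs, SAP 3.8.1 says: "It will be summarized by preferred term and treatment group for the double-blind period". AEs leading to discontinuation are handled the same way. Neither sentence gives an onset window.
- **Later events.** SAP 3.8.1 defines NEAEs as starting or worsening after the last study-drug dose of the treatment period, and summarises them in the follow-up safety population. SAP 3.2.3 counts olanzapine as study drug, and Protocol 9.1 states: "Olanzapine dosing will continue uninterrupted through the end of the study".

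**The concern.** With bedtime dosing, a cut-off on the calendar date of the last tablet leaves almost all of that tablet's post-dose day outside the window. A subject who takes the tablet at night, wakes with an adverse event and takes no more has an onset one day too late to be a double-blind TEAE. The same applies to anything that begins on the day of a completer's final visit.

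Safety and tolerability is the trial's only secondary objective (Protocol 6.2), and the by-arm double-blind TEAE tables are the main randomised evidence for it. The rule removes from those tables the events closest to stopping treatment. It also makes the SAP inconsistent: a laboratory or ECG finding at an ET visit a few days after the last tablet can count as on-treatment while an adverse event starting that day does not.

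**Working it through.** The plan gives no figure to reproduce here; the check is day arithmetic. Let L be the date of the last samidorphan/placebo dose.

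**Step 1. Where each day falls.** A completer's final visit is the day after the last dose, L+1. In Protocol Table 3, Visit 39 is at week 41 or 65 and Visit 40 at week 42 or 66, against a final visit at week 39 or 63. They are therefore 14 and 21 days after the final visit, at L+1+14 = L+15 and L+1+21 = L+22.

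| Onset or assessment | Day | Double-blind TEAE (SAP 3.8.1) | No later than L+7 (SAP 6.1 limit) |
|---|---|---|---|
| Evening of last dose | L | yes | yes |
| Morning after last dose | L+1 | no | yes |
| Completer's final visit | L+1 | no | yes |
| Last day allowed for an on-treatment ET visit | L+7 | no | yes |
| Visit 39 | L+15 | no | no |
| Visit 40 | L+22 | no | no |

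The exception is a tablet taken after midnight, where L is already the new calendar day.

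**Step 2. How much of the last dosing day is covered.** Assume tablets are taken between 20:00 and 23:00. The time left before midnight is then 4 hours to 1 hour of 24: 4/24 = 17% down to 1/24 = 4%.

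**Step 3. Completers.** For a 9-month subject, Visit 26 is one of four post-randomisation laboratory visits (10, 14, 20, 26) and one of three ECG visits (14, 20, 26) in Protocol Table 2. Protocol 13.1 makes a clinically significant laboratory value an adverse event. If that event is dated to the Visit 26 sample, the value is summarised under double-blind treatment and the event is not.

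**Step 4. Events in neither summary.** Let Z be the date of the last olanzapine dose within the treatment period. A TEAE needs onset on or before L. An NEAE needs onset or worsening after Z. If a subject stops only the blinded tablet and stays on olanzapine in the treatment period, Z is later than L, and an event starting in the Z − L days from L+1 to Z meets neither rule. Where both drugs stop on the same night, Z = L and there is no gap.

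**Step 5. Size.** The documents give no rate of stopping for an adverse event and no share of such events with onset after L. For illustration only, assume that 5% to 15% of 135 subjects per arm stop for an adverse event and that 10% to 50% of those events start after L:

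- low: 135 × 0.05 × 0.10 = 0.7
- high: 135 × 0.15 × 0.50 = 10.1

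That is about 1 to 10 subjects per arm whose stopping event lies outside the TEAE window. The width of the range shows that the documents cannot fix the number.

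**Step 6. With a 7-day lag.** Onsets on L+1 to L+7, including a completer's final visit, move into the double-blind tables. Visits 39 and 40 stay outside.

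**The case against.** The strongest reply is that little is lost from reporting. Excluded events go to the NEAE summary, and SAP 7 makes by-arm presentation the default. SAEs are listed for the whole study. SAP 3.3 tabulates reasons for discontinuation by arm whatever the onset date, and SAP 3.7.5 compares time to stopping study drug. C-SSRS results are summarised for the double-blind and follow-up periods (SAP 3.8.7). All of this stands: events are misallocated, not hidden. The double-blind TEAE tables are still incomplete, and none of these outputs restores them.

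A second reply is that the 7 days in SAP 6.1 belong to a visit-mapping rule and do not define a risk period for adverse events. That is correct, so 7 days is a choice. It is nevertheless the SAP's own on-treatment limit, and Protocol 8.4.4 recognises that samidorphan can blunt opioid analgesia for several days after dosing. A zero lag has no support in either document.

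Third, the rule is the same in both blinded arms. Protocol 5.3 places most samidorphan-related events in the first 2 weeks of treatment, which here precede randomisation, and Protocol 5.2.1 reports no sign of withdrawal after abrupt stopping. This counts against assuming a bias between arms, but it does not justify the cut-off.

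Four stronger readings are tempting, and the documents do not support them:

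- **The SAE and AE-discontinuation tables lose the same events.** SAP 3.8.1 sets no onset window for them. A programmer might apply the TEAE rule, the only double-blind attribution rule given, but the text does not require it.
- **Everything in follow-up falls in neither summary because olanzapine continues.** The NEAE rule refers to the last dose within the treatment period, and olanzapine is taken together with the blinded tablet, so for a completer the two dates coincide.
- **Worsening events are deliberately excluded.** The window speaks only of starting, but the TEAE definition just before it includes worsening. This is loose wording.
- **The NEAE denominator should be all randomised subjects.** SAP 3.2.3 reads: "Follow-up safety population is defined as subjects who entered into the follow-up period or have any newly emergent adverse events". Admitting subjects because they had an event can distort a percentage, but an all-randomised denominator counts subjects not observed in follow-up as event-free. That choice is debatable.

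**Conclusion.** The point holds for the by-arm double-blind TEAE tables. With bedtime dosing, the stated rule excludes events that start the day after the last samidorphan/placebo tablet, including one that makes a subject stop and one found at a completer's final visit. An event that starts on or before the last-dose date and later leads to stopping is still counted.

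For the SAE and AE-discontinuation tables the plan is ambiguous. The gap between the TEAE and NEAE rules is confined to subjects who stop the blinded tablet alone while still in the treatment period.

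The number of events affected cannot be derived, and the range of about 1 to 10 subjects per arm rests wholly on assumed rates. A reader might infer that the tables would favour the arm with more early stops. That would need different stopping rates or onset patterns by arm, and the documents give neither. The rule is worth correcting before unblinding because it misplaces events in the main safety comparison and is easy to change.

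**What to change.** In SAP 3.8.1, state one window for the double-blind TEAE, SAE and AE-discontinuation tables: adverse events that start or worsen from the first double-blind dose through 7 days after the last samidorphan/placebo dose, matching SAP 6.1. Define NEAEs as starting or worsening after that day, keyed to the last samidorphan/placebo dose and not to study drug in general, and say that they are shown by treatment group.

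The cost is SAP wording and one date derivation. Protocol 13.4 already collects adverse events through the safety follow-up visit, so no new data are needed. The downside is that a few events beginning shortly after the tablets stop will count as on-treatment, in both arms alike.
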